5.3. Major Secondary Endpoints

5.3.1. Definition

Formulae to be used for derived variables, including data conversions, are provided in the tables below.

Note that for time-to-event parameters the actual date or date times that the endpoint is met will be used. For the time-to-event parameters the subject will be censored using a time-to value equal to the maximum time across all subjects in the following cases:

- death,
- if a subject had not resolved the influenza symptoms at time of hospitalization and/or during hospitalization, and no further data on symptom resolution is available

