5.3.1.2. Other Patient Reported Outcome

Measurement	Formula
Daily activities resumption	
Daily activities resumption will be assessed once daily by means of the question 'Over the past 24 hours, how much has influenza interfered with your ability to carry out your daily activities?'
 
The responses will be dichotomized: 'Not at all' and 'A little bit' will be considered as category “returned to daily activities” and responses 'Somewhat', 'Quite a Bit' and 'Very much' will be considered in category “not returned to daily activities”.

Time to return to daily activities (hours) [Time-to event]	The time to return to daily activities is defined as the time in hours from initiation of study treatment to the first of a successive series of 2 recordings in which the response is considered as returned to daily

	
activities. The 2 successive recordings may have been done over 3 scheduled successive analysis timepoints, in case of 1 missing in between timepoint.
 
In case the return to daily activities is not achieved, data will be censored.
 
Censoring will be done as follows:
 
 1) Last non-missing record indicates return to daily activities (but insufficient recordings) 
Censoring will be done at the last non-missing record
 2) Last non-missing record does not indicate return to daily activities 
Censoring will be done one day (24 hours) after the last non-missing record.
 
The time to return to daily activities is calculated as: (Date and time of event (actual) or censoring - date and time of first dose of study drug)/3600, rounded to one decimal.
																														

Patient Global Impression of Severity of Influenza symptoms
	
The PGIS captures daily influenza symptom severity from the subjects’ perspective per timepoint. Responses will be categorized as: “No Flu symptoms today”, “Mild”, "Moderate", "Severe" or “Very Severe”.
																														

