	
The following rules will be applied in the order described below to deal with missing values before calculating the Viral titer AUC:
 
 • If the baseline value is missing, then the mean baseline value over all subjects in the ITT-i set will be used. • If a single or sequential intermediate values (not the baseline value) are missing, then the missing value will be replaced by linear interpolation of the two adjacent values. Note: this is done automatically when applying the trapezoidal summation rule. If the Day 10 value is missing, but there is an assessment after Day 10, then this value will be used to interpolate the value for Day 10. • If the Day 10 value is missing, and there are no values available after Day 10, then it will be imputed with the last observed post-baseline value (LOCF). 
Note: In case no post baseline value is available the AUC will be missing.

Time to viral negativity by qRT-PCR (days) [Time-to event]
	
The time to viral negativity is defined as the time (in days) from first study drug intake until a subject is considered influenza A viral negative. This is the first timepoint of two consecutive timepoints with confirmed negative nasal MT swab ie, the first and next assessment are equal to 'negative' (ignoring missing values). In case the first 'negative' is the last available assessment the subject is considered to have reached viral negativity at this last assessment. If this doesn't occur, a subject will be censored at the time of the last observed non-negative swab + 1 day. Note that for deriving the time to viral negativity by qRT-PCR every subject is considered positive at baseline.

Time to viral negativity by viral culture (days) [Time-to event]
	
The algorithm for Time to viral negativity by viral titer is similar as 'Time to viral negativity by viral load' but viral titer assessments are used instead.

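### For viral negativity and return to daily activities, SAP 5.3.1 and the endpoint rows give different censoring times after death or hospitalization, with no stated precedence

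*SAP*

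**What the plan says.** The opening text of SAP 5.3.1 contains a note and a rule. The note reads: "Note that for time-to-event parameters the actual date or date times that the endpoint is met will be used". The rule reads: "For the time-to-event parameters the subject will be censored using a time-to value equal to the maximum time across all subjects". It has two triggers. One is death. The other is "if a subject had not resolved the influenza symptoms at time of hospitalization and/or during hospitalization", combined with there being no further data on symptom resolution.

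Two sets of endpoint rows below that text carry their own censoring and mention neither death nor hospitalization:

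- **Return to daily activities (5.3.1.2).** "In case the return to daily activities is not achieved, data will be censored". If the last record shows a return, censoring is at that record. If it does not: "Censoring will be done one day (24 hours) after the last non-missing record".
- **Viral negativity by qRT-PCR (5.3.1.4).** The event is the first of two consecutive negative swabs. If a first negative is the last available swab, "the subject is considered to have reached viral negativity at this last assessment". If negativity does not occur, "a subject will be censored at the time of the last observed non-negative swab + 1 day". The culture endpoint uses the same algorithm, except that "viral titer assessments are used instead".

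Elsewhere the SAP ties the maximum-time rule to the endpoint. In the primary definition (5.2.1) and the individual-symptom rows (5.3.1.1) it sits in a list that applies only when symptoms have not resolved. The fever row (5.3.1.3) does the same and rewrites the hospitalization trigger in terms of fever and fever data.

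**The concern.** The two treatments mean different things. Censoring at the last swab plus one day takes the subject out of the risk set early and says nothing about what followed. Censoring at the maximum time keeps the subject in the risk set throughout, in effect as someone who never recovered. Two programmers following the SAP in good faith could build different analysis datasets.

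The hospitalization trigger is also keyed to the wrong data. Protocol 3.1 asks sites to keep up all scheduled assessments in hospitalized subjects where feasible, and swabs run to Day 14. Protocol 9.2.1.2 exempts intubated subjects and those with a decreased level of consciousness from the questionnaires. A subject can therefore have a full set of swabs and no symptom diary, and the missing diary would decide how the swab endpoint is censored.

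The subjects concerned are among the sickest. Time to viral negativity has its own superiority objective (Protocol 2.1.1, SAP 1.1) and is analysed by several time-to-event methods (SAP 5.3.2.4). If deaths or admissions differ between arms, the choice of rule could shift the comparison.

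**Working it through.** The plan gives no figure for this rule, so there is nothing to reproduce. The check is to apply both rules to the same subject.

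| Subject | Endpoint row | 5.3.1 rule |
|---|---|---|
| No negative swab, last positive swab Day 6, then dies | Censored Day 6 + 1 = Day 7 | Censored at maximum time |
| Last daily-activity record is a non-return on Day 5, then dies | Censored Day 5 + 24 h = Day 6 | Censored at maximum time |
| Swabs negative Days 6 and 10; admitted Day 11 with symptoms unresolved and no later symptom data, or dies Day 20 | Event at Day 6 | Maximum time if read literally; event at Day 6 if the preceding note protects endpoints already met |

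The first two cases conflict on any reading, because the subject has no event and both rules apply. The third conflicts only on the literal reading.

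**Size of the conflict for event-free subjects.** Let f be the share of an arm that is event-free and triggered, c the day the row would censor them, and S(t) the Kaplan-Meier estimate under the row's rule, with no other censoring. If all are censored before any event, the maximum-time rule gives (1 − f)·S(t) + f. The difference is

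f + (1 − f)·S(t) − S(t) = f × (1 − S(t)).

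If they are censored later, at c, the difference is f × (1 − S(t)/S(c)), which is smaller. So f × (1 − S(t)) is a ceiling.

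For illustration only, assume log-logistic times to negativity with median 6 days and scale 0.5, observed on the planned swab days. Then S(14) is about 0.155 and 1 − S(14) about 0.845. The range for f is also assumed.

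| f (assumed) | Ceiling on the Day 14 difference, f × 0.845 |
|---|---|
| 0.5% | 0.4 points |
| 1% | 0.8 points |
| 3% | 2.5 points |
| 5% | 4.2 points |
| 10% | 8.5 points |

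In head counts, the planned infected set is 720 × 0.85 / 2 = 306 per arm, so 3% is about 9 subjects and 5% about 15.

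**Literal reading of 5.3.1.** Under the same assumed distribution, suppose a share f meets a trigger whatever their event status, and any observed event is overridden. By simulation, the event share falls from about 84.5% to 84.2%, 83.5%, 81.9%, 80.2% and 76.0% for f of 0.5%, 1%, 3%, 5% and 10%. The Day 14 proportion still positive rises from about 0.155 to 0.158, 0.165, 0.181, 0.198 and 0.240.

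**The case against.** A reader might infer that the SAP discards viral-negativity or daily-activity events that were actually observed. The documents do not support that as a statement of fact. The note just before the rule says that actual times are used when the endpoint is met. The daily-activities row censors only when return is not achieved, and the viral row only when negativity does not occur. Read together, these point to censoring only subjects without the event. The note is not a clear safeguard, since it may mean only actual rather than planned times, as the similar note in SAP 5.4.1 seems to. But overriding an observed event remains one literal reading of an ambiguous paragraph.

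Three further points limit the matter. The individual symptoms, the improvement-from-baseline version of the symptom endpoint and fever are not exposed; only return to daily activities and the two viral-negativity endpoints are. The hospitalization trigger needs symptoms unresolved at or during the stay and no later symptom data, so a subject who had recovered symptomatically before admission does not meet it. And SAP 5.1.1 confines the confirmatory hierarchy to the primary endpoint, complications and hospital admission.

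All of this stands. None of it resolves the event-free case, where both rules apply, their times differ and nothing says which governs.

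**Conclusion.** The text is wrong as written, at minor priority. For event-free subjects who die or meet the hospitalization trigger, SAP 5.3.1 and the rows in 5.3.1.2 and 5.3.1.4 prescribe different censoring times without stated precedence, and the hospitalization trigger uses symptom status and symptom data instead of the endpoint's own. That much rests on the text alone.

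The size rests on assumptions. The documents give no rate for the triggers in this population. The 0.5% to 10% range and the time-to-negativity distribution are assumed, and the tabulated differences are ceilings that require every counted subject to be both triggered and event-free. The true number is probably small. Any effect on the treatment comparison would need the share or timing of affected subjects to differ between arms, which cannot be judged from the documents. The primary test, its significance level and the sample size are unaffected.

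**What to change.** Reword the rule in SAP 5.3.1 so that a subject is censored at the maximum time only if the endpoint in question had not been reached before death or hospitalization and no later data on that endpoint are available. This follows the pattern of the fever row. It removes the symptom-based trigger for endpoints that do not measure symptoms, and it settles that an observed event keeps its actual time.

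Then add a clause to both the daily-activities row (5.3.1.2) and the viral-negativity row (5.3.1.4) saying which rule takes precedence for event-free subjects who die or are hospitalized. Through its reference to the qRT-PCR algorithm, the culture endpoint would follow.

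The cost is one reworded sentence and two short clauses, made before unblinding. No new data collection is needed and no figure in the plan changes.

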5.3.1.1. Symptoms of Influenza (Flu-iiQ™ Module 1)

Measurement	Formula
Time to resolution of cough (hours) [Time-to-event]	
This parameter will be calculated using the symptom of cough included in Module 1 of the Flu-iiQ™.
 
Cough is considered resolved depending on pre-existence of the symptom.
 
 • The symptom is pre-existing: 
 ○ The symptom is considered resolved if post-baseline severity is equal or lower than the pre-existing severity • The symptom is not pre-existing: 
 ○ The symptom is considered resolved if its severity is scored at most mild post-baseline 
The time of resolution is the first of a successive series of 3 recordings in which the symptom for each of the 3 assessments is considered resolved (as defined above). The 3 successive recordings may have

	
been done over 4 scheduled successive analysis timepoints, in case of 1 missing in between timepoint.
 
In case the symptom is not resolved, data will be censored.
 
Censoring will be done as follows:
 
 1) Last non-missing record(s) indicate resolution of symptom (but insufficient recordings to meet the time to resolution) 
Censoring will be done at the first record of resolution from the last series of recordings of resolution of the symptom
 2) Last non-missing record does not indicate resolution of the symptom 
Censoring will be done after the last observation, which is 08:00 on the same day if the last observation was a diary entry from 00:01 until 02:00, 20:00 on the same day if the last observation was a diary entry from 02:01 until 14:00, and 08:00 the next day if the last entry was a diary entry from 14:01 until 00:00.
 3) Additionally, in the following cases the subject will be censored using a time-to equal to the maximum time across all subjects: 
 ○ death, ○ if a subject had not resolved the symptoms at time of hospitalization and/or during hospitalization, and no further data on symptom resolution is available
Time to resolution of sore throat (hours) [Time-to-event]	This parameter is defined similarly as the time to resolution of cough and will be calculated using the symptom of sore throat included in Module 1 of the Flu-iiQ™.
Time to resolution of headache (hours) [Time-to-event]	This parameter is defined similarly as the time to resolution of cough and will be calculated using the symptom of headache included in Module 1 of the Flu-iiQ™.
Time to resolution of nasal congestion (hours) [Time-to-event]	This parameter is defined similarly as the time to resolution of cough and will be calculated using the symptom of nasal congestion included in Module 1 of the Flu-iiQ™.
Time to resolution of feeling feverish (hours) [Time-to-event]	This parameter is defined similarly as the time to resolution of cough and will be calculated using the symptom of feeling feverish included in Module 1 of the Flu-iiQ™.

Time to resolution of body aches and pains (hours) [Time-to-event]	This parameter is defined similarly as the time to resolution of cough and will be calculated using the symptom of body aches and pains included in Module 1 of the Flu-iiQ™.
Time to resolution of fatigue (hours) [Time-to-event]	This parameter is defined similarly as the time to resolution of cough and will be calculated using the symptom of fatigue included in Module 1 of the Flu-iiQ™.
Time to resolution of neck pain (hours) [Time-to-event]	This parameter is defined similarly as the time to resolution of cough and will be calculated using the symptom of neck pain included in Module 1 of the Flu-iiQ™.
Time to resolution of interrupted sleep (hours) [Time-to-event]	This parameter is defined similarly as the time to resolution of cough and will be calculated using the symptom of interrupted sleep included in Module 1 of the Flu-iiQ™.
Time to resolution of loss of appetite (hours) [Time-to-event]	This parameter is defined similarly as the time to resolution of cough and will be calculated using the symptom of loss of appetite included in Module 1 of the Flu-iiQ™.
Composite symptom score for systemic symptoms	
The systemic symptoms included in Module 1 of the Flu-iiQ™ consist of: headache, feeling feverish, body aches and pains, fatigue, neck pain, interrupted sleep, and loss of appetite.
 
The subject's composite symptom score for systemic symptoms per datetime is defined as the mean of the severity (0-3 scale) of the non-missing systemic symptoms for each datetime the questionnaire was filled. Note: a higher value is considered a worse value.
 
If more than 50% of the items to construct a Composite symptom score are missing, the value for that composite score is coded as missing (ie, 4 or more items missing).

Composite symptom score for systemic symptoms change from baseline	Composite symptom score for systemic symptoms post-baseline value – composite symptom score for systemic symptoms baseline value.
Composite symptom score for respiratory symptoms	
The respiratory symptoms included in Module 1 of the Flu-iiQ™ consist of: cough, sore throat, and nasal congestion.
 
The subject's composite symptom score for respiratory symptoms per datetime is defined as the mean of the severity (0-3 scale) of the non-

	
missing respiratory symptoms for each datetime the questionnaire was filled. Note: a higher value is considered a worse value.
 
If more than 50% of the items to construct a Composite symptom score are missing, the value for that composite score is coded as missing (ie, 2 or more items missing).

Composite symptom score for respiratory symptoms change from baseline	Composite symptom score for respiratory symptoms post-baseline value – composite symptom score for respiratory symptoms baseline value.
Time to resolution of the 7 primary influenza-related symptoms considering improvement from baseline (hours) [Time-to-event]	
A symptom is considered resolved depending on pre-existence of the symptom:
 
 • the symptom is pre-existing 
 ○ If baseline response > pre-existing response, then the symptom is considered resolved if post-baseline severity is lower than the baseline severity ○ If baseline response ≤ pre-existing response, then the symptom is considered resolved if post-baseline severity is ≤ the pre-existing severity • the symptom is not pre-existing 
 ○ The symptom is considered resolved if its severity is scored at most mild post-baseline 
The time to resolution will be derived in the same way as the primary endpoint (Section 5.2.1).

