### 4.1. Inclusion Criteria

Each potential subject must satisfy all of the following criteria to be enrolled in the study:

1. Male or female, 13 to 85 years of age, inclusive. Note: Adolescent subjects (13 to 17 years) will be enrolled in selected countries and study sites consistent with local regulations.
2. Present to the clinic with symptoms suggestive of a diagnosis of acute influenza and have at least 1 respiratory symptom and at least 1 systemic symptom, both scored as at least “moderate” if the symptom did not pre-exist before influenza onset, or scored worse than usual if the symptom pre-existed as determined by subject’s ratings on Module 1 of the Flu-iiQ™ and the Pre-existing Symptom Questionnaire in the ePRO device. Symptoms must include the following by category:
  1. Respiratory symptoms: cough, sore throat, nasal congestion
  2. Systemic symptoms: headache, body aches or pain, feverishness, fatigue
3. Tested positive for influenza A infection after the onset of symptoms, using a rapid influenza diagnostic test (RIDT) or, if available, a PCR-based or other rapid molecular diagnostic assay.

4. Not be in need of hospitalized medical care at screening. Emergency room or hospital observation status for an anticipated duration of <24 hours is not considered hospitalization as long as a determination of the need for hospitalization has not been made.
5. Enrollment and initiation of study drug treatment  $\leq 72$  hours after onset of influenza symptoms.
6. Must sign an ICF/assent form (or their legally acceptable representative must sign) indicating that he or she understands the purpose of, and procedures required for, the study and is willing to participate in the study. Assent is also required of children capable of understanding the nature of the study, typically subjects 7 years of age and older. Subjects must sign a separate ICF/assent form if he or she agrees to provide an optional DNA sample for research (where local regulations permit). Refusal to give consent for the optional DNA research sample does not exclude a subject from participation in the study.
7. Before randomization, a woman must be either:
  - a. Not of childbearing potential defined as:
    - Premenarchal  
*A premenarchal state is one in which menarche has not yet occurred.*
    - Postmenopausal  

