### **11.1. Analysis Sets**

The efficacy endpoints will be analyzed on the Intent-to-Treat-infected (ITT-i) set, consisting of all subjects who were randomized, treated and had a confirmed influenza A infection, and will be analyzed by treatment arm as randomized.

The primary endpoint will also be analyzed on the Per Protocol set, consisting of all subjects in the ITT-i set without major protocol deviations that have an effect on efficacy and who were not prematurely unblinded during the study.

All safety endpoints will be evaluated on the Safety population, consisting of all subjects who received at least one dose of study drug and will be analyzed by treatment arm as treated.

Pharmacokinetic data will be evaluated on subjects in the ITT-i set who received pimodivir. Subjects will be excluded from the population PK analysis if their data do not allow for accurate assessment of the PK parameters (eg, incomplete administration of the study drug; missing information of dosing and sampling times).

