2.2.2. Efficacy Analysis Sets

Efficacy will be analyzed on the intent-to-treat infected (ITT-i) set and by randomized treatment. The primary efficacy endpoint will also be analyzed on the Per Protocol set. The primary efficacy endpoint and the two most important secondary endpoints (ie, 'Incidence of treatment-emergent adjudicated influenza complications' and 'Incidence of hospital admission 28 days after treatment initiation') will also be analyzed on the intent-to-treat non-infected (ITT-ni) set and by randomized treatment.

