- if a subject had not resolved the influenza symptoms at time of hospitalization and/or during hospitalization, and no further data on symptom resolution is available

Subjects not completing the pre-existing symptom questionnaire, or completing it after study day 1, will have values for each individual question imputed with the median response category of all subjects in the ITT-i set.

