5.3.2.1. Symptoms of Influenza (Flu-iiQ™ Module 1)

Composite symptoms scores (systemic symptoms, respiratory symptoms)

The actual composite symptom scores and changes from baseline will be shown descriptively and by mean (SE) plots per analysis visit and timepoint.

Time to resolution of: cough; sore throat; headache; nasal congestion; feeling feverish; body aches and pains; fatigue; neck pain; interrupted sleep; loss of appetite; the 7 primary influenza-related symptoms considering improvement from baseline

The time to resolution of cough, sore throat, headache, nasal congestion, feeling feverish, body aches and pains, fatigue, neck pain, interrupted sleep, loss of appetite, and the 7 primary influenza-related symptoms, improvement from baseline will be analyzed by Kaplan-Meier analysis, Gehan-Wilcoxon test, log-rank test, AFT model, and Cox proportional hazards model.

The AFT and Cox models will include the fixed categorical effects for treatment (with placebo as the reference) and stratification factors and the baseline symptom score as a continuous variable.

If the baseline symptom score is missing, then the baseline score will be imputed as the median score from all subjects in the ITT-i set.

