5.3.2.3. Clinical Outcomes

Incidence of treatment-emergent adjudicated influenza complications, hospital admission rate, incidence of treatment-emergent adjudicated influenza complications including hospital admission, and incidence of all-cause mortality

The number and percentage of subjects in each parameter category and subcategory will be tabulated and listed. All subjects in the applicable analysis set will be counted for the denominator of the proportion.

The occurrence (yes/no) for hospital admission rate, incidence of treatment-emergent adjudicated influenza complications including hospital admission, and incidence of all-cause mortality will be analyzed using logistic regression as described above (Section 5.3.2).

The occurrence (yes/no) of influenza complications will be analyzed using logistic regression as described above, for each of the following categories:

- the overall influenza complications
- the pulmonary complications,
- the extrapulmonary complications
- the pulmonary complications including sinusitis and otitis
- the infectious complications
- the non-infectious complications
- the major complications
- the minor complications

Time to resolution of fever

Time to resolution of fever will be analyzed similarly as time to return to daily activities.

A subgroup analysis will be done based on the subset of subjects with fever at baseline (temperature $\geq 37.0^{\circ}\text{C}$) as recorded as part of the on-site vital signs assessment.

Temperature recordings made by the subject on the ePRO device lower than 34°C or higher than 43°C will not be included in the analysis.

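### Individual-symptom resolution times count subjects who never had the symptom, and the fever rule counts acetylsalicylic acid whatever its indication; neither has a supportive analysis

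*SAP*

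**What the plan says.** **Individual symptoms.** Protocol 11.1 sets the analysis set, "The efficacy endpoints will be analyzed on the Intent-to-Treat-infected (ITT-i) set", and SAP 2.2.2 follows it: "Efficacy will be analyzed on the intent-to-treat infected (ITT-i) set and by randomized treatment". SAP 5.3.1.1 defines time to resolution of cough and applies the same rule to the other nine Flu-iiQ symptoms. A symptom that did not pre-exist is resolved when scored none or mild after baseline. A pre-existing one is resolved when back to its earlier level or lower. The event is dated from this point: "first of a successive series of 3 recordings in which the symptom for each of the 3 assessments is considered resolved (as defined above". Baseline scores play no part in this rule.

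Protocol 4.1 (criterion 2) requires only that subjects "have at least 1 respiratory symptom and at least 1 systemic symptom" of sufficient severity. SAP 5.3.2.1 plans Kaplan-Meier, Gehan-Wilcoxon, log-rank, AFT and Cox analyses. Only the last two allow for the starting level, through treatment "and stratification factors and the baseline symptom score as a continuous variable". SAP Table 6 has no subgroup for presence of a Flu-iiQ symptom at baseline.

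**Fever.** SAP 5.3.1.3 assumes that everyone is febrile at baseline. It requires three successive self-recorded temperatures below 37.0°C on days free of antipyretics, in line with Protocol 2.1.2. Antipyretics are found by ATC code or generic name, and acetylsalicylic acid is one of the names, with no condition on indication or dose (also SAP 4.6). A record with no start date is taken as started before the trial, and one with no end date as continuing to its end. Diary-reported use blocks the whole day. One supportive analysis exists: "A subgroup analysis will be done based on the subset of subjects with fever at baseline" (SAP 5.3.2.3). It leaves the antipyretic rule unchanged.

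**The concern.** A subject with no headache at baseline who never develops one has nothing to resolve, yet enters the headache analysis as an event at the first diary entry. Such events are unrelated to treatment. They shorten the medians in both arms and weaken the contrast. Subjects like this are expected by design, because entry needs only two of seven listed symptoms. Neck pain, interrupted sleep and loss of appetite are not on the entry list at all, yet each has its own endpoint.

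The fever problem runs the other way. Coronary artery disease and stroke are qualifying conditions (Protocol 4.1, criterion 12), so long-term acetylsalicylic acid is plausible in this population. If its recorded use covers the whole temperature follow-up, the subject is a non-resolver whatever the thermometer shows. That lengthens the medians and again weakens the contrast, inside the baseline-fever subset as well. Use that starts later or is intermittent blocks only the days concerned.

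Both endpoints were added at Health Authority request (Protocol Amendment 1). As planned, a reader could not tell a null result from dilution, or a short median from absence of the symptom.

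**Working it through.** **Inputs.** From Protocol 11.3: 600 subjects randomised 1:1, log-logistic times, scale 0.55, 25% reduction. From Protocol 9.6.4: self-recorded temperature until Day 14 (336 h). Assumed, because the documents do not give them: share lacking a symptom, share later developing it, share on daily acetylsalicylic acid, and a placebo median of 55 h. The scale and effect were set for the 7-symptom composite and are borrowed here.

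**Calibration on the plan's own figures.** For a log-logistic shift, Gehan-Wilcoxon power is about Φ(√(N/12) × (−ln 0.75)/scale − 1.96).

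- Scale 0.5213: Φ(3.902 − 1.96) = 97.4%; the plan has 97.3% (Protocol Table 3, SAP Table 2).
- Scale 0.5867: Φ(3.467 − 1.96) = 93.4%; the plan has 93.3%.
- Scale 0.55: Φ(3.699 − 1.96) = 95.9%. The text of Protocol 11.3 says 90%, so the undiluted reference below is about 96%, not 90%.

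**Closed form for dilution.** Suppose a share q is tied at one extreme, either resolved at the first record or never resolved. Only pairs with both members outside that share carry the effect, so the expected statistic scales by (1 − q)². The tie correction scales the variance by 1 − q³. The noncentrality is multiplied by r = (1 − q)²/√(1 − q³).

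- q = 10%: r = 0.810; Φ(2.997 − 1.96) = 85%.
- q = 20%: r = 0.643; Φ(2.377 − 1.96) = 66%.
- q = 30%: r = 0.497; Φ(1.837 − 1.96) = 45%.
- Restriction to the other 70% (N = 420): Φ(3.094 − 1.96) = 87%.

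**Simulation.** 4,000 trials per scenario (Cox: 800), unstratified tests, two-sided 5%, first diary record at 2–13 h and then every 12 h. Monte Carlo error is at most 0.8 points (Cox 1.8). With nobody lacking the symptom: Gehan 96%, log-rank 90%, Cox with baseline score 91%.

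Power (%) for an individual symptom, all subjects versus baseline-symptomatic subset (a dash means not tabulated):

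| Lacking symptom | Of these, develop it | Gehan | Log-rank | Cox |
|---|---|---|---|---|
| 10% | none | 85 vs 93 | 83 vs 86 | – |
| 30% | none | 44 vs 86 | 61 vs 77 | 62 vs 78 |
| 30% | half | 77 vs 86 | 78 vs 76 | 76 vs 75 |
| 50% | half | 55 vs 73 | 67 vs 62 | 65 vs 60 |

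Medians (placebo/pimodivir) are 61/47 h in the subset. With 30% lacking the symptom, they are 40/31 h in all subjects if none develop it and 52/40 h if half do. As a check, with q = 30% the overall median is the (0.5 − 0.3)/0.7 = 28.6th percentile of symptomatic subjects, which is (0.286/0.714)^0.55 = 0.604 of their median. 55 × 0.604 = 33 h, plus about 6 h for the diary grid (the same 6 h that takes 55 to 61), gives about 39 h.

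Power (%) for fever by share on daily acetylsalicylic acid:

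| Start of recorded daily use | Test | 0% | 10% | 20% | 30% |
|---|---|---|---|---|---|
| First dose | Gehan | 96 | 85 | 67 | 48 |
| First dose | Log-rank | 89 | 58 | 36 | 23 |
| Day 4 | Gehan | – | 94 | 93 | 92 |
| Day 4 | Log-rank | – | 85 | 82 | 80 |
| First dose, 70% febrile subset | Gehan | 87 | 71 | 52 | 34 |

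Use from first dose raises the placebo median from 61 h to 68, 79 and 98 h. If use starts on Day 7 there is no visible loss (Gehan 95–96%, log-rank 90%). The closed form with N = 420 gives 71, 51 and 34% for the febrile subset.

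**The case against.** No rule is broken. The protocol fixes ITT-i, defines resolution without a baseline condition, and excludes antipyretic use without an exception for indication; the SAP implements this literally. The protocol objectives for these endpoints are only to investigate, and no formal claim rests on them. An all-subject comparison is valid and captures symptoms that start after baseline, which a subset misses. All of this stands, and it is why ITT-i should remain the main analysis.

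The AFT model carries the baseline score and yields time ratios and bootstrapped medians (SAP 5.3.2), and composite scores with change from baseline are also planned. This helps only in part. With the baseline score fitted in a log-logistic AFT model, the time ratio is 0.80 in all subjects against 0.78 in the subset when 30% lack the symptom and half develop it, and 0.82 against 0.78 when 50% lack it and half do. When 30% lack it and none develop it, the ratio is 0.85 against 0.79 and power 62% against 85%. SAP 2.3 allows further subgroup analyses in a separate plan, but that is permission, not a commitment.

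The subset is not better for every test: log-rank and Cox lose a little once half develop the symptom. The shares are unsourced. Cardiovascular disease is one of three qualifying routes at ages 13–65, and at least 72 adolescents are targeted, so 30% on daily acetylsalicylic acid may be high. These limits stand. They bear on the size of the effect, not on its existence.

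**Conclusion.** Both halves hold, at minor severity. The rules are explicit and can make the secondary results misleading. Affected subjects should be balanced by randomisation, so the consequence is dilution and distorted medians, not bias in favour of either arm. The endpoints are outside the confirmatory sequence (SAP 5.1.1), so the primary conclusion and Type I error are untouched.

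The size depends wholly on assumed shares. For symptoms the loss falls mainly on Gehan-Wilcoxon. It is large when subjects lacking the symptom never develop it and much smaller when half do. For fever it is large only if recorded use runs from about the first dose, and small or absent if use starts on Day 4 or later.

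**What to change.** 1. **Symptoms.** Keep the ITT-i analysis. For each symptom, prespecify an analysis in ITT-i subjects whose observed baseline score is unresolved under the SAP's own rule: moderate or severe if not pre-existing, or above the pre-existing level. Report it beside the all-subject result. Decide membership on observed scores only. Under SAP 5.2.1, subjects without a timely pre-existing symptom questionnaire "will have values for each individual question imputed with the median response category of all subjects in the ITT-i set", and SAP 5.3.2.1 also imputes missing baseline scores by the median. Subjects with either score missing stay in the all-subject analysis alone.
2. **Fever.** Add a sensitivity analysis, overall and in the planned baseline-fever subset, in which acetylsalicylic acid recorded for an indication other than fever or pain does not count as antipyretic use. Check diary-reported use against the concomitant medication record where possible.

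**Cost.** SAP wording, one flag per symptom and one indication filter; no new data and no protocol change. The symptom flag needs a comparison that the SAP already makes for the improvement-from-baseline endpoint: "If baseline response > pre-existing response, then the symptom is considered resolved if post-baseline severity is lower than the baseline severity". The indication of each therapy is already recorded (Protocol 8). The downsides are smaller subsets, slightly less power for log-rank and Cox in some settings, symptoms of later onset appearing only in the all-subject analysis, and diary entries, for which no indication is described and which the filter cannot reach.
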